7.8 Study Completion

All subjects enrolled in this study are expected to complete all scheduled visits through the 6 Months Follow-Up Visits. A Study Completion CRF should be completed at this visit. In situations where there is an ongoing device related adverse event, subjects will be followed until resolution of that adverse event or determination that the subject's condition is stable, at which point the Study Completion CRF should be completed.

7.9 Study Suspension and Termination

The study may be terminated when all of the requirements of the investigational plan have been fulfilled. Subjects will be considered to have completed all study requirements following completion of the 6 Months Follow-Up Visits. The clinical sites will be considered to have completed the study requirements at the end of the clinical site close out monitoring visit. The study will be considered terminated when

all close out visits have been completed and all Sponsor and Investigator reports have been issued.

Sponsor, the Investigators, or the EC may suspend or terminate the study early at any time. If the study is suspended or terminated prematurely, all currently enrolled subjects will be withdrawn from the study and a Study Completion/Termination CRF will be completed. If there is an ongoing event related to the device or therapy, the subject will be followed until resolution of that adverse event or determination that the subject's condition is stable.

The Sponsor reserves the right to terminate the study, but intends only to exercise this right for valid scientific or business reasons, or reasons related to the protections of the study subjects. Investigators and ECs will be notified in writing in the event of study termination. Possible reasons for study termination include, but are not limited to the discovery of unexpected, significant, or unacceptable risk to subjects enrolled in the study.

The Sponsor reserves the right to stop the enrollment of subjects at a clinical site at any time after the clinical site initiation visit if no subjects have been enrolled, or if the clinical site has multiple deviations from the clinical investigational plan without justification, or fails to follow remedial actions. Possible reasons for suspending or terminating a clinical site may include, but are not limited to:

- Investigator non-compliance.
- Repeated failure to complete or submit CRFs in a timely manner.
- Failure to obtain written informed consent.
- Failure to report SAEs or USADEs to the Sponsor and/or EC within 24 hours of knowledge.
- Failure to control or account for investigational products used.

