7.7 Early Subject Withdrawal

Subjects may be withdrawn early from the study for a number of reasons, including but not limited to:

- Subject request.
- Investigator request.
- Subject lost to follow up.
- Subject death.
- Intolerable adverse events.

If a subject is discontinued from the study early, a Termination CRF will be completed describing the reason for discontinuation. The Investigator should make all attempts to conduct a visit within 10 days (± 4 days) after withdrawal from the study. If a subject has withdrawn consent for the study, or is lost to follow-up, the completion of this visit is not imperative. In situations where study withdrawal is due to an adverse event, subjects will be followed until resolution of that adverse event or determination that the subject's condition is stable.

In case of an Early Subject Withdrawal the subject will be assessed for adverse events, if any, and medication use. This will be documented on an Unscheduled Visit CRF.

In case the Early Subject Withdrawal happened at a study specific follow-up visit (see Table 1. Schedule of Events) no Unscheduled Visit CRF need to be completed.

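### Section 7.9 withdraws every enrolled patient on any suspension or early stop, so treated patients lose the rest of their scheduled follow-up, including the 6-month primary VAS

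*Combined protocol and SAP*

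**What the plan says.** Section 7.9 gives the power to halt broadly: "Sponsor, the Investigators, or the EC may suspend or terminate the study early at any time". The sponsor adds that it "intends only to exercise this right for valid scientific or business reasons, or reasons related to the protections of the study subjects", so a halt need not be a safety matter. The consequence is fixed: "If the study is suspended or terminated prematurely, all currently enrolled subjects will be withdrawn from the study". The section keeps one form of follow-up: "If there is an ongoing event related to the device or therapy, the subject will be followed until resolution of that adverse event", or until the patient's condition is judged stable.

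Section 7.7 covers early withdrawal in general. "The Investigator should make all attempts to conduct a visit within 10 days" (± 4 days) of withdrawal. On content it says: "In case of an Early Subject Withdrawal the subject will be assessed for adverse events, if any, and medication use". The VAS is not named there, but the result goes on an Unscheduled Visit form, and sections 7.5.8 and Table 1 include the VAS at an unscheduled visit.

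Three other parts of the protocol depend on follow-up to 6 months:
- The primary endpoint (5.2) is the change in VAS from baseline to the 6-month visit.
- Section 7.8 states: "All subjects enrolled in this study are expected to complete all scheduled visits through the 6 Months Follow-Up Visits".
- Section 7.10 defines the ITT-B set with the stated purpose of capturing adverse events before the 6-month visit.

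**The concern.** Withdrawing patients at a halt makes sense when it ends exposure to a treatment still being given. Here the schedule (7.5 and Table 1) has a single treatment visit, and section 9 has the needle and electrode removed at its end. That treatment is given once is inferred from this schedule; the protocol does not say so in words. Once that visit is over, the patient only completes questionnaires and is asked about medication and adverse events. Withdrawal takes away that information and nothing else.

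Two things are at stake. First, even a brief administrative hold would, as written, end the route to the primary outcome for every treated patient not yet at 6 months. No section provides for re-entry when a suspension is lifted. Second, 7.9 names the discovery of unacceptable risk as a possible reason to stop. That is when later events in treated patients are most informative, yet an event that begins after the exit visit, or an ongoing event not judged related, has no further scheduled follow-up. Section 13 gives no rule for missing 6-month values, so the analysis plan does not make up for the loss.

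**Working it through.** **Inputs.** From 7.3: difference 20 mm (40 against 60 mm), SD 30 mm, two-sided t-test at 5%, power 90%, losses 20%, 62 per group. From the summary: 12 months of enrolment and 6 months of follow-up. From 7.5.7: 6-month window of ± 20 days. **Assumptions, not in the documents:** even accrual, treatment on the day of enrolment, equal arms, and no resumption after the halt.

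**Step 1. The plan's own figure.** With d = 20/30 = 0.667, the exact two-sample t-test needs 48.26, so 49 per arm. Then 49 / (1 − 0.20) = 61.25, so 62 per arm. The stated size reproduces and is not in dispute.

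**Step 2. Who is caught by a stop at month s.** Enrolled = 124 × min(s, 12) / 12. Past 6 months = 124 × (s − 6) / 12, bounded between 0 and 124. Truncated = the difference.

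**Step 3. Power after 20% losses.** Patients per arm = 0.8 × count / 2. The rule as written uses those past 6 months; the alternative follows all enrolled patients to 6 months.

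| Stop at month | Enrolled | Past 6 months | Truncated | Power, rule as written | Power, enrolled patients followed |
|---|---|---|---|---|---|
| 6 | 62 | 0 | 62 | none (no 6-month data) | 63% |
| 9 | 93 | 31 | 62 | 36% | 81% |
| 12 | 124 | 62 | 62 | 63% | 91% |
| 15 | 124 | 93 | 31 | 81% | 91% |

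Any stop from month 6 to month 12 catches 62 patients. The planned loss allowance is 0.20 × 124 = 24.8, about 25 in total, and cannot absorb that.

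**Step 4. Month 12, like for like.** Before losses: 31 per arm gives 73%, and 62 per arm gives 96%. After 20% losses: 24 to 24.8 per arm gives 62–63%, and 49 to 49.6 per arm gives 90–91%.

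**Step 5. How far the exit visit softens this.** Patients within 20 days of their 6-month date at the stop number 124 × 20 / 365 = 6.8, about 7. An exit visit up to 14 days later extends this to 124 × 34 / 365 = 11.6, about 12. If all of them give an in-window VAS, the month-12 count rises from 62 to between 69 and 74, or 34.5 to 37 per arm. Power is then about 78–81% before losses. After 20% losses (27.6 to 29.6 per arm) it is about 68–71%.

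**The case against.** The strongest reply is that the protocol already softens the rule, and that the harm may never occur. Much of this stands.

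- A reader might infer that data are thrown away. The documents do not support that. Nothing says recorded values are deleted, patients past 6 months are unaffected, and the 1-, 2- and 4-month VAS values already collected remain.
- A reader might infer that nothing after the halt is seen. That is also too strong. The exit visit covers events up to that point, and ongoing related events are followed. Section 8.8 requires serious incidents associated with a device to be reported, with no tie to a study visit. None of these is scheduled follow-up for new events, for ongoing events judged unrelated, or for late events that fall short of a reportable incident.
- The exit visit can include a VAS. For most truncated patients, however, it would fall well before 6 months, and Step 5 shows the limited gain.
- Setting 73% against 90% would be a mismatch, because the planned 90% already allows for 20% losses. The fair pairs are those in Step 4.
- If a hold is lifted, the trial might resume or replace patients. The documents neither provide for this nor rule it out, so final power after a hold cannot be derived. After a permanent stop, the planned power is no longer the target, and the figures measure only the information given up.
- No interim analysis or stopping rule is described, so the rule matters only in an unplanned halt. The documents give no basis for a probability.
- Section 7.8 describes an uninterrupted study. It should not be read as a flat contradiction of 7.9.

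These points reduce the size of the concern. They do not explain why treated patients should leave data collection because the study is paused or stopped.

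**Conclusion.** The point holds in a limited form. Section 7.9 applies one unconditional consequence to suspension and termination alike. It thereby ends the remaining scheduled assessments, including the 6-month VAS, for patients whose treatment visit is already over. This sits poorly with the primary endpoint and with the purpose stated for the ITT-B set.

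A trial that runs to completion is unaffected. If the study is halted, the worst case at month 12 is 62 patients truncated and, after 20% losses, power of about 62–63% against 90–91%. That rests on even accrual, no resumption and no in-window exit VAS. With every possible in-window exit VAS obtained, power is about 68–71%. The loss of late safety observation is partial and cannot be quantified from the documents. The change is worth making because it is cheap and because 6-month visits missed during a halt cannot be recovered later.

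**What to change.** Amend 7.9 so that a suspension or early termination does not by itself withdraw already treated patients from data collection. They keep the scheduled VAS and adverse event assessments through 6 months, unless they withdraw consent or the ethics committee or authority requires otherwise. State separately what a temporary suspension and a permanent termination mean for data collection.

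Align 7.7, so that any exit visit for patients who do leave names the VAS alongside adverse events and medication use. Align 7.10, so that the ITT-B purpose agrees with the follow-up kept after a halt. What happens to treatment during a halt is for the sponsor and the ethics committee, and this point proposes nothing on it.

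The cost is about one paragraph of text plus two cross-references. If a halt occurs, the sponsor pays for at most about 6 months of remaining visits. If none occurs, the cost is nil.

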7.10 Definition of Population for Analyses

We define 3 different subject populations for analysis:

1. Intent-to-Treat (ITT)

- All subjects who receive any treatment of the groups (Experimental or Control)

2. Per Protocol (PP)

- All subjects who receive treatment of the study and complete the Primary Effectiveness Assessment (Primary Endpoint defined above).

3. ITT-Baseline (ITT-B)

- All subjects who complete baseline assessment. In order to capture AEs that occur prior to the 6 months follow-up visit.

8. – SAFETY ASPECTS

The definitions presented in this section allow for a clear understanding of adverse event data collection and reporting requirements.

Medical Device

Any instrument, apparatus, implement, machine, appliance, implant, software, material or other similar or related article.

Intended by the manufacturer to be used, alone or in combination, for human beings for one or more of the specific purpose (s) of:

- Diagnosis, prevention, monitoring, treatments or alleviation of disease,
- Diagnosis, monitoring, treatment, alleviation of, or compensation for, an injury,
- Investigation, replacement, modification, or support of the anatomy or of a physiological process,
- Supporting or sustaining life,
- Control of conception,
- Disinfection of medical devices and

Which does not achieve its primary intended action in or on the human body by pharmacological, immunological or metabolic means, but which may be assisted in its intended function by such means. The term 'medical device' is usually defined by national regulations.

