7.2 Randomization Process

The clinical investigation will be single-blind. The assignment to the type of surgical treatment is carried out randomly and open for the investigators but not for

the patients. Randomization will be done with concealment of the randomization sequence and it takes place after informed consent has been signed.

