7.3 Sample Size and justification

Pain reduction at least thirty millimeters between the baseline visit and the 6 months visit in patients assigned to the experimental group evaluated by the Visual Analogue Scale (VAS). Pain reduction of twenty millimeters less in the experimental group than in the control group since the baseline visit and the 6 months visit evaluated by the Visual Analogue Scale (VAS).

To achieve a power of 90.00% to detect differences in the contrast of the null hypothesis $H_0: \mu_1 = \mu_2$ through a bilateral T-Student Test for two independent samples, taking into account that the level of significance is 5%, and assuming that the mean of the difference in VAS of the 6-month radiofrequency plus steroid group is 40 mm, the average of the control group is 60 mm and the standard deviation of both groups is 30 mm, with an estimate of losses of the 20%, it will be necessary to include 62 patients per group, total of 124 patients.

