7.5.2. Baseline* (within 30 days from Screening Visit)

At this clinic visit the subject will undergo the following evaluations:

- Randomization.
- Eligibility criteria will be re-evaluated.
- Any change of medication will be collected.

- Subjects will be asked to fill out standard questionnaires to assess (VAS, ODI, SF-12 and DN4).
- Subjects will be assessed for possible adverse events, if any.
- AP and lateral view lumbar imaging.
- Screening failures will be collected.

*Baseline and Treatment visits could be at the same time.

All applicable information will be documented on a CRF.

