7.5.8. Unscheduled Visit

At this clinic visit the subject will undergo the following evaluations:

- Any change of medication will be collected.
- Subjects will be asked to fill out standard questionnaires to assess (VAS, ODI, SF-12, DN4 and PGI-I).
- Subjects will be assessed for possible adverse events, if any.
- Study completion (if applicable).
- Adverse event monitoring.
- Deviation monitoring.
- Subject questionnaire of treatment satisfaction.

All applicable information will be documented on a CRF.

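### The set labelled Intent-to-Treat in section 7.10 contains only treated patients and is not tied to the assigned arm, and section 13 names no set for the primary test

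*Combined protocol and SAP*

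**What the plan says.** Section 7.10 defines three sets.

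- **ITT:** "All subjects who receive any treatment of the groups (Experimental or Control").
- **Per Protocol:** treated subjects who complete the primary effectiveness assessment.
- **ITT-B:** subjects who complete the baseline assessment. Its stated purpose is to capture adverse events before the 6-month visit.

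None of the three mentions randomisation or says in which arm a patient is counted. Section 13 gives the primary test (t-test or Mann-Whitney on the 6-month change in VAS) but names no set. Sections 5.2 and 7.3 name none either.

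On the path from allocation to treatment:

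- Section 7.2: "The assignment to the type of surgical treatment is carried out randomly and open for the investigators", though not for patients. The sequence is concealed. On timing it says only that "it takes place after informed consent has been signed".
- Section 7.5.2 places randomisation at the Baseline visit, where also "Eligibility criteria will be re-evaluated" and screening failures are recorded. A footnote adds that "Baseline and Treatment visits could be at the same time".
- Section 7.5.3 otherwise gives treatment its own visit, with a 15-day window either way.
- Section 7.7 allows withdrawal at the investigator's request.

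On follow-up, section 7.8 states that "All subjects enrolled in this study are expected to complete all scheduled visits through the 6 Months Follow-Up Visits". For early withdrawals, section 7.7 asks for adverse events and medication use, recorded on the Unscheduled Visit form. Section 13 has no rule for a missing 6-month VAS.

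**The concern.** Intention-to-treat keeps the comparison that randomisation created, because nothing that happens after allocation decides who is counted or in which arm. The 7.10 set lacks that property in two ways. A patient randomised but not treated drops out of it, and a patient given the other arm's treatment has no defined arm. Concealing the sequence protects enrolment. It does not protect against exclusion after allocation by someone who knows the arm.

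The other two sets do not repair this. Per Protocol is also limited to treated patients. With no missing-data rule, a complete-case 6-month test would use nearly the same patients in ITT and Per Protocol, so one is little check on the other. ITT-B comes close to all randomised patients, but it is defined by completing baseline, is tied to adverse events, and is not assigned to the primary test.

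At stake are the label on the primary result, a choice of set left open until the data are seen, and 6-month VAS values that cannot be recovered later if they are not collected.

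**Working it through.** **1. The plan's sample size.** Inputs from 7.3: means 40 and 60 mm (difference 20 mm), SD 30 mm, two-sided 5%, power 90%, losses 20%. The noncentral t calculation gives 48.26, so 49 per arm, and 49/0.8 = 61.25, so 62 per arm and 124 in total. The stated figure is reproduced. After 20% losses, 62 × 0.8 = 49.6, about 50 per arm, with power 91.0%. No number in the plan is disputed here.

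**2. Who is counted, by set.**

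| Patient | ITT | Per Protocol | ITT-B |
|---|---|---|---|
| Randomised, baseline done, not treated | out | out | in (adverse-event purpose) |
| Given the other arm's treatment | in, arm undefined | in if endpoint complete, arm undefined | in, arm undefined |

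**3. Possible bias of the treated-only set when there is no true difference.** The documents give no untreated rate and no link to prognosis, so everything here except the 62 per arm, SD 30 mm and 20% losses (applied at random) is assumed. Suppose one arm loses its *k* patients with the worst prognosis, and prognosis has correlation *r* with the outcome. With *f* = *k*/62, φ the normal density and *z* its *f*-quantile:

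bias ≈ *r* × 30 × φ(*z*)/(1 − *f*)

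SE ≈ 30 × √[1/(0.8(62 − *k*)) + 1/(0.8 × 62)]

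type I error ≈ Φ(−1.96 + bias/SE) + Φ(−1.96 − bias/SE)

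- *k* = 3: *f* = 0.0484 and φ(*z*)/(1 − *f*) = 0.1005/0.9516 = 0.1056. Bias is 0.95 mm (*r* = 0.3) or 1.58 mm (*r* = 0.5). SE is 6.10 mm. Type I error is 5.3% or 5.8%.
- *k* = 6: *f* = 0.0968 and φ(*z*)/(1 − *f*) = 0.1713/0.9032 = 0.1897. Bias is 1.71 or 2.85 mm. SE is 6.18 mm. Type I error is 5.9% or 7.5%.

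Simulation of 40,000 null trials per setting agrees:

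| Patients lost | Bias (mm) | Type I error |
|---|---|---|
| 1 of 62, one arm | 0.3 to 0.5 | 5.0% |
| 3 of 62, one arm | 0.9 to 1.6 | 5.2% to 6.0% |
| 6 of 62, one arm | 1.7 to 2.8 | 5.7% to 7.6% |
| 3 in each arm, or *r* = 0 | about 0 | 4.9% to 5.3% |
| 3 or 6 of 62, one arm, but kept and followed to 6 months | −0.04 to 0.02 | 5.0% to 5.1% |

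The last row assumes that being untreated does not alter the outcome under the null.

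**4. Cost of analysing everyone as assigned.** If *k* of 62 experimental patients go untreated and have the control mean, the expected difference is 20 × (62 − *k*)/62.

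| *k* | Difference (mm) | Power, 50 per arm | Power, 62 per arm |
|---|---|---|---|
| 0 | 20.0 | 91.0% | 95.8% |
| 3 | 19.0 | 88.1% | 93.9% |
| 6 | 18.1 | 84.6% | 91.4% |

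Controls receive a steroid, so untreated patients may do worse than the control mean, and dilution may then be larger than shown.

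**The case against.** The strongest reply is that the harm is hypothetical. Treatment is a single procedure that may take place on the day of randomisation, so few patients need go untreated. Patients do not know their arm, so their own withdrawal before treatment should not depend on it. Both arms share the sedation, caudal needle, catheter and fluoroscopic guidance, so failure of access should be similar. Type I error near 7.6% needs six patients lost from one arm only, exactly the six with the worst prognosis, at a correlation of 0.5. No passage predicts that. All of this stands, and it limits the weight of the point. It does not mend the definition, the missing assigned-arm wording or the unnamed primary set.

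The plan also covers part of the follow-up. Section 7.8 expects every enrolled subject through 6 months, and the Unscheduled Visit in 7.5.8 includes the VAS: "Subjects will be asked to fill out standard questionnaires to assess (VAS, ODI, SF-12, DN4 and PGI-I"). But for a withdrawn patient that visit falls about 10 days after withdrawal, so it does not supply the 6-month value.

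A reader might infer three stronger things that the documents do not support:

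- **That randomisation precedes the eligibility re-check.** Section 7.5.2 is a bullet list and states no order.
- **That the trial is sized on assignment and therefore contradicts 7.10.** Section 7.3 does say "Pain reduction at least thirty millimeters between the baseline visit and the 6 months visit in patients assigned to the experimental group", but this rests on one word. The power sentence speaks only of groups, and 7.3 is unclear about its target reductions.
- **That the primary result will be biased.** Nothing in the plan shows that exclusions will occur, or that they will be one-sided.

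**Conclusion.** Section 7.10 is wrong as written: a treated-only set carries the Intent-to-Treat label, no set is tied to the assigned arm, and the primary test has no named set. Because allocation is open to investigators, this leaves a route for exclusion with the arm known.

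The documents do not allow the bias to be sized, and it is probably small. It is about zero if exclusions are few, balanced or unrelated to prognosis. Under the assumed one-arm, worst-prognosis loss it is about 0.9 to 1.6 mm with 3 of 62 and 1.7 to 2.8 mm with 6 of 62; the upper value is 2.8/20 = 14% of the planned difference. This is a low-end should-fix: the effect is uncertain, but the correction is cheap and the uncollected VAS could not be recovered.

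**What to change.** - **7.10:** define ITT as all randomised patients, analysed in the arm assigned. Rename the current set the treated set and keep it as a supporting analysis. Keep ITT-B for adverse events.
- **13:** name the redefined ITT as the set for the primary test. Prespecify one rule for a missing 6-month VAS, with a sensitivity analysis.
- **7.5.2:** state that randomisation follows the eligibility re-check and the baseline questionnaires.
- **7.7:** state, in line with 7.8, that untreated or withdrawn randomised patients are still asked for the scheduled VAS through 6 months unless they withdraw consent. This is the main remedy, because a wider set without outcomes only moves the problem into the missing data.

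Setting never-treated patients to no change from baseline is not a safe missing-data rule. With 6 of 62 lost from one arm and *r* = 0.3, it gives a bias of about +0.3 mm if both arms improve by 10 mm, −2.1 mm at 30 mm and −4.4 mm at 50 mm (type I error about 9%). The last two are worse than leaving the patients out (about +1.7 mm).

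The cost is wording in four sections, VAS follow-up of a few more patients, and the dilution shown above. The sample size stays at 62 per group.
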